## 4 Endpoints

The following study endpoints will be evaluated in all subjects enrolled in the NIRTRAKS Post-Market Study.

### 4.1 Primary Endpoint

The primary endpoint for this study is TVF, which is defined as a composite of cardiac death, target vessel MI, or clinically driven TVR by percutaneous or

### 4.2 Secondary Endpoints

#### 4.2.1 TVF at 9 Months

#### 4.2.2 All Cause Death at 30 Days, and 1, 2 and 3 Years

#### 4.2.3 Cardiac Death at 30 Days, and 1, 2 and 3 Years

Cardiac death is defined as any death due to proximate cardiac cause (e.g. MI, low-output failure, fatal arrhythmia), unwitnessed death and death of unknown cause, and all procedure-related deaths, including those related to concomitant treatment.

#### 4.2.4 All Cause MI at 30 Days, and 1, 2 and 3 Years

4.2.5 MI is defined using the Academic Research Consortium (ARC) definitions (see Appendix 1-P).

#### 4.2.6 Target Vessel MI at 30 Days, and 1, 2 and 3 Years

Target vessel MI is defined as any MI attributed to the target vessel.

#### 4.2.7 Clinically Driven TLR at 30 Days, and 1, 2 and 3 Years

Clinically-driven target lesion revascularization (TLR) is defined as any revascularization at the target lesion associated with positive functional ischemia study or ischemic symptoms and an angiographic minimal lumen diameter stenosis  $\geq 50\%$  by quantitative coronary angiography (QCA), or revascularization of a target lesion with diameter stenosis  $\geq 70\%$  by QCA without either angina or a positive functional study.

#### 4.2.8 Clinically Driven TVR at 30 Days, and 1, 2 and 3 Years

Clinically-driven TVR is defined as any revascularization in the target vessel that is associated with positive functional ischemia study or ischemic symptoms AND an angiographic minimal lumen diameter stenosis  $\geq 50\%$  by QCA, or revascularization of a target vessel with diameter stenosis  $\geq 70\%$  by QCA without either angina or a positive functional study.

#### 4.2.9 Acute Success Rates

*Device success* is defined as the attainment of  $<50\%$  final residual stenosis of the target lesion using only the NIRxcell Stent System.

*Lesion success* is defined as the attainment of  $<50\%$  final residual stenosis of the target lesion using any percutaneous method.

*Procedure success* is defined as attainment of  $<50\%$  residual stenosis of the target lesion and no in-hospital death, MI or TLR.

#### **4.2.10 Stent Thrombosis at Discharge, 30 Days, and 1, 2 and 3 Years**

*Acute stent thrombosis* is defined as a thrombotic event occurring between 0 and 24 hours after stent implantation.

*Subacute stent thrombosis* is defined as a thrombotic event occurring between 1 and 30 days after stent implantation.

*Late stent thrombosis* is defined as a thrombotic event occurring between 30 days to 1 year after stent implantation.

Three separate categories of stent thrombosis using the ARC classification are recognized and defined in Appendix 1-P.

## 5 Study Design

This is a prospective, post-marketing, non-randomized, multi-center, single-arm clinical study to collect additional information about the safety and effectiveness of the NIRxcell Stent System in the treatment of *de novo* stenotic lesions in native coronary arteries in the US population. A total of 131 subjects will be enrolled in up to 15 sites in the US. The expected duration of subject enrollment is approximately 12 months. Clinical follow-up for all subjects will occur at 30 days, 9 months and 1, 2 and 3 years post-index stenting procedure. An unscheduled follow up may be conducted as clinically warranted.

### 5.1 Control of Systematic Error/Bias

By the nature of the type of the proposed study, blinding of the investigator and/or subject is not possible. However, several measures will be implemented for minimization of systematic error/bias:

- Basic screening will be completed by investigational sites of all potential candidates. Subjects who fail to meet the *clinical* inclusion and exclusion criteria will not be included in this study. Subjects who have met all the *clinical* inclusion and exclusion criteria will then be screened for angiographic eligibility criteria.
- All subjects who undergo angiographic screening will be entered onto the screening log. The screening log will include all subjects who have signed the informed consent.
- Measurements made by angiography will be standardized by use of an angiographic core laboratory. The core laboratory measurements will be used in all cases for purposes of data analysis.

In determining subject eligibility for the study, the investigator's assessment of pre-procedure angiographic parameters will be used. However, the angiographic core laboratory will provide feedback to the sponsor concerning accuracy of assessments in relation to inclusion criteria such as lesion parameters and anatomic location.

- Electrocardiogram (ECG) tracings analysis will be standardized by use of an ECG core laboratory. The ECG core laboratory readings will be used in all cases for purposes of data analysis.
- Clinical monitors will verify subjects' data and ensure compliance with Good Clinical Practice (GCP), clinical protocol and other study requirements, according to the guidelines set forth in HCRI's monitoring standard operating procedures (SOP).
- An independent clinical events committee (CEC) will adjudicate all clinical endpoint events and investigator-reported adverse events that have the potential to be a clinical endpoint event. The CEC adjudication results will be used in all cases for purposes of data analysis.

### 5.2 Eligibility, Exclusions and Subject Discontinuations

All subjects presented to the angiographic suite for possible coronary artery revascularization are potential study candidates and will be screened for eligibility, and consented for possible inclusion. Every effort will be made to establish eligibility of the participants prior to enrollment. Prior to enrollment, subjects will have screening clinical laboratory, medical

history and physical exams to verify qualification into the study. If conducted within the appropriate time windows, and the subjects meet the pre-angiography inclusion and exclusion criteria, the screening results will also serve as baseline parameters. Angiographic eligibility will be based solely on angiography performed at the time of index procedure. Once a subject has signed the informed consent, angiographic eligibility has been confirmed, and the NIRxcell Stent System introduced into the subject's body, the subject is considered to be enrolled. Subjects who do not meet **all** inclusion (general and angiographic) criteria or meet **any** of the exclusion criteria should not be enrolled in the study. All subjects enrolled will be evaluated, regardless of sequence of treatment that ensues.

Once a subject has been enrolled in the study, he/she may withdraw his/her consent to participate in the study at any time without prejudice. Participation in this clinical investigation is entirely voluntary.

[figure not shown]
Possible reasons for subject discontinuation include but are not limited to the following:

- Subject death
- Subject voluntary withdrawal
- Subject withdrawal by physician as clinically-indicated
- Subject lost-to follow-up as described below

Subjects withdrawn after treatment will not be required to undergo follow-up after withdrawal; however, they will still be considered part of the subject cohort.

All subjects enrolled in the study are considered eligible for follow-up and will be required to adhere to the follow-up schedule outlined in Section 9. If a subject cannot be contacted for a follow-up assessment and follow-up information cannot be obtained, he/she will be counted as "missed contact" for that specific schedule. Attempts shall be made to contact the subject in next follow-up schedule. A subject will be considered "lost to follow-up" only after the last scheduled follow-up assessment for that subject (3 years). If a subject is lost to follow-up, the methods used to attempt to contact the subject should be documented. At least 3 attempts should be made to contact the subject through all available routes, and a certified letter should be sent to the permanent address in file.

Figure 1 summarizes the above steps and follow-up period.

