### 11.1 Definition of Adverse Event and Serious Adverse Event

#### 11.1.1 Adverse Event

An AE is defined as any untoward medical occurrence, unintended disease or injury, or untoward clinical signs (including abnormal laboratory findings) in subjects, users or other persons, whether or not related to the study device.

**NOTE 1:** This definition includes events related to the study device or the comparator.

**NOTE 2:** This definition includes events related to the procedures involved.

**NOTE 3:** For users or other persons, this definition is restricted to events related to the study device.

In this study, AEs shall be assessed and documented at IC signing. All AEs are to be recorded through the end of the study on the appropriate subject case report forms and followed through to their resolution regardless of time window.

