4.3.2 Analysis of Primary Endpoint

The primary endpoint for this study is TVF, which is defined as a composite of cardiac death, target vessel MI, or clinically driven TVR by percutaneous or surgical methods within 3 years post-procedure.

No formal statistical test will be performed, as this study is descriptive only. The TVF rate at 3 years and the exact two-sided 95% confidence intervals will be provided. In addition, the TVF at 3 years will be estimated for all ITT subjects by generating the two-sided 95% confidence

interval of the Kaplan-Meier estimate of the primary endpoint rate; subjects not experiencing the endpoint will be censored at 3 years post-procedure or day of withdrawal, whichever is earlier. Finally, the same analysis will be carried out on the PP population (secondary analysis).

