2 Denominator for 9-Month contact includes patients who had 9-month visit form filled or patients who have reached 300 (270+30) days after procedure (data export date - procedure date) and excludes patients who died or withdrew before 300 days.

3 Denominator for 1-year contact includes patients who had 1-year visit form filled or patients who have reached 395 (365+30) days after procedure (data export date - procedure date) and excludes patients who died or withdrew before 395 days.

4 Denominator for 2-year contact includes patients who had 2-year visit form filled or patients who have reached 760 (730+30) days after procedure (data export date - procedure date) and excludes patients who died or withdrew before 760 days.

5 Denominator for 3-year contact includes patients who had 3-year visit form filled or patients who have reached 1125 (1095+30) days after procedure (data export date - procedure date) and excludes patients who died or withdrew before 1125 days.

Table 4 Patient Disposition

	ITT Subjects (N=xx subjects)	Per Protocol Subjects (N=xx subjects)
	n (%)	n (%)
Enrolled	xx (xx.xx%)	xx (xx.xx%)
Completed the study	xx (xx.xx%)	xx (xx.xx%)
Not completed all required follow-up visits	xx (xx.xx%)	xx (xx.xx%)
Primary reason for not completed		
Withdrew consent	xx (xx.xx%)	xx (xx.xx%)
Lost to follow-up	xx (xx.xx%)	xx (xx.xx%)
Adverse event	xx (xx.xx%)	xx (xx.xx%)
Death	xx (xx.xx%)	xx (xx.xx%)
Lack of efficacy	xx (xx.xx%)	xx (xx.xx%)
Protocol violation	xx (xx.xx%)	xx (xx.xx%)
Physician decision	xx (xx.xx%)	xx (xx.xx%)
Study cancelled	xx (xx.xx%)	xx (xx.xx%)
Other	xx (xx.xx%)	xx (xx.xx%)

Table 5 Demographic and Medical History – Intention-to-Treat Analysis Set

Characteristics	ITT Subjects (N=xx subjects)	95% CI
Demographics		
Age (yrs)		
Mean±SD (N)	xx.xx±xx.xx (xx)	[xx.xx, xx.xx]
Median (Q1, Q3)	xx.xx (xx.xx, xx.xx)	
Range (min, max)	(xx.xx, xx.xx)	
Male	xx.xx% (xx/xx)	[xx.xx%, xx.xx%]
Ethnicity		
Hispanic or Latino	xx.xx% (xx/xx)	[xx.xx%, xx.xx%]
Not Hispanic or Latino	xx.xx% (xx/xx)	[xx.xx%, xx.xx%]
Race		
American Indian or Alaska Native	xx.xx% (xx/xx)	[xx.xx%, xx.xx%]
Asian	xx.xx% (xx/xx)	[xx.xx%, xx.xx%]
Black or African American	xx.xx% (xx/xx)	[xx.xx%, xx.xx%]
Native Hawaiian or Other Pacific Islander	xx.xx% (xx/xx)	[xx.xx%, xx.xx%]
White	xx.xx% (xx/xx)	[xx.xx%, xx.xx%]
Other	xx.xx% (xx/xx)	[xx.xx%, xx.xx%]
Medical History/Risk Factor		
Previous MI	xx.xx% (xx/xx)	[xx.xx%, xx.xx%]
Previous PCI	xx.xx% (xx/xx)	[xx.xx%, xx.xx%]

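### Follow-up is not required after any withdrawal, including one decided by the physician, and nothing provides for collecting later events or vital status

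*Protocol*

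**What the plan says.** Protocol 5.2 sets the rule, and SAP 2.2.4 repeats it: "Subjects withdrawn after treatment will not be required to undergo follow-up after withdrawal". Such subjects nonetheless remain in the cohort. The reasons for discontinuation are introduced by "Possible reasons for subject discontinuation include but are not limited to the following", so the list is open. It names death, the subject's own withdrawal, loss to follow-up, and "Subject withdrawal by physician as clinically-indicated".

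The disposition shell in SAP section 5 (Table 4) has rows for the main reason for not completing. They include "Adverse event", "Lack of efficacy", protocol violation and physician decision.

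Scheduled follow-up is by telephone (Protocol 9, SAP 2.2.6). For a missed contact, attempts continue, and a subject is declared lost only after the 3-year assessment (Protocol 5.2). Protocol 11.1.1 wants adverse events "followed through to their resolution regardless of time window".

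For TVF, SAP 4.3.2 gives a rate with an exact interval, plus a Kaplan-Meier estimate in which "subjects not experiencing the endpoint will be censored at 3 years post-procedure or day of withdrawal, whichever is earlier". The rate uses subjects who had the event or had adequate follow-up (Protocol 12.8, note to SAP Table 1.1a).

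**The concern.** There is no continuing study treatment to stop. When a physician exits a subject for clinical reasons, the stent stays in place and only the telephone calls end. A subject who is merely hard to reach is pursued for 3 years, while a symptomatic subject withdrawn by a physician need not be contacted again.

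Reasons tied to the subject's condition make it plausible that the censoring is informative. Kaplan-Meier treats a censored subject as having the same later risk as those who remain. If the exited subjects are in fact at higher risk, the TVF estimate is too low. A subject exited after a revascularization already counts as a TVF. A later death, infarction or stent thrombosis in that subject would still be missed, and each is a separate 3-year endpoint.

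The analysis does not repair this. The multiple imputation in Protocol 12.8 uses five baseline covariates and not the reason for exit, and SAP 4.3.2 has no imputation. SAP Table 3 leaves out of each compliance denominator the subjects who withdrew before that window closed, so the compliance figures would not show these exits.

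**Working it through.** **The plan's own figure.** SAP 4.1 enrolls 65 and allows about 7% loss per year: 65 x 0.93^3 = 52.3, which agrees with the stated 52 or so. About 13 subjects are therefore planned to lack 3-year data, against 0.232 x 52 = 12.1 expected TVF events in the evaluable group. The documents do not say how many of the 13 would be condition-related exits, so 13 is a ceiling for this mechanism and not an estimate of it.

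**Inputs for the Kaplan-Meier error.**
- N = 65 (SAP 2.2.2), so one subject is 1/65 = 1.54 points.
- 3-year TVF risk p = 23.2% (Protocol 12.1), taken as the risk of subjects who remain.
- Assumed, not in the documents: m = 2 to 6 condition-related exits while event-free, with k = 1.5 to 2 times the risk.

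**Exit near day 0 (largest case).** Understatement = (m/65) x (k - 1) x p.
- Low: 2/65 x 0.5 x 23.2 = 0.36 points.
- High: 6/65 x 1.0 x 23.2 = 2.14 points.

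**Exit at 1 year.** Only the remaining risk matters. Protocol 12.1 puts half of long-term events in year 1. Its conversion from 5 to 3 years (a factor of 0.5 + 0.25 = 0.75) implies that 0.5/0.75, or two-thirds, of 3-year events fall in year 1. I use one-half and two-thirds as the range, and apply k to the remaining risk.
- One-half past: remaining risk if event-free = 11.6/88.4 = 13.1%.
- Two-thirds past: 7.73/84.53 = 9.1%.
- Low: 2/65 x 0.5 x 9.1 = 0.14 points. High: 6/65 x 1.0 x 13.1 = 1.21 points.

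These are 39% to 57% of the day-0 values (9.1/23.2 and 13.1/23.2), or roughly half.

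**Direction of the binomial rate.** This rule keeps withdrawn subjects who had events and drops those who were event-free, which by itself pushes the rate up. Take loss unrelated to risk at 7% per year, true TVF of 23.2%, and events spread evenly over 3 years:
- Mean retention at the time of an event = (1 - 0.93^3)/(3 x 0.0726) = 0.1956/0.2177 = 0.899, where 0.0726 = -ln 0.93.
- Events observed = 0.232 x 0.899 = 0.2085.
- Event-free completers = 0.768 x 0.8044 = 0.6178.
- Expected rate = 0.2085/(0.2085 + 0.6178) = 25.2%, about 2.0 points too high.

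This upward error is about as large as the top of the Kaplan-Meier range and runs the other way. With informative exits added, the net sign for the binomial rate cannot be fixed from the documents.

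**Scale.** An observed 12/52 (23.1%) has an exact two-sided 95% interval of 12.5% to 36.8%. The Kaplan-Meier error is small beside that.

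**The case against.** The text says follow-up is not required; it does not forbid it, and withdrawn subjects stay in the cohort. That is correct, but no provision makes later collection happen.

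A reader might infer more than the documents support:
- That adverse event and lack of efficacy are grounds for withdrawal. They appear only as rows in an empty reporting shell. The discontinuation text names only the physician's decision, although its list is open.
- That exiting a subject with a failed stent lowers the TVF rate. A TVF event before exit is counted whatever happens later. Only event-free exits can affect TVF.
- That every resulting error flatters the device. This follows for Kaplan-Meier if exited subjects are at higher risk, but not for the binomial rate, as shown above.
- That the rule contradicts other text in Protocol 5.2. The sentence on evaluating all enrolled subjects concerns the treatment received, and the duty to keep the schedule is the general rule to which withdrawal is an exception. Protocol 11.1.1 is in some tension with the rule, but it concerns following recorded adverse events to resolution.

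Two further points stand. The SAP is descriptive with no formal test, so no pass or fail decision is at risk. Also, the SAP cites protocol Version 3.0 while the protocol available is version 1.2, so the latest protocol wording cannot be checked; SAP 2.2.4 does carry the same sentence.

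**Conclusion.** The gap is real and modest. Physician-decided withdrawal can end data collection in a study where there is no treatment to stop, and neither planned TVF estimate corrects for exits related to risk. Under the stated assumptions the Kaplan-Meier TVF rate would be too low by at most about 0.4 to 2.1 points with exit near day 0, and by about 0.1 to 1.2 points with exit at 1 year. The number of such exits and their excess risk are assumptions; that they are above average at all is an inference from the reasons for exit. The loss of later deaths, infarctions and stent thromboses from the 3-year secondary endpoints rests on the same mechanism and cannot be sized from the documents. No direction is claimed for the binomial TVF rate. The case for change is that avoidable bias can be removed cheaply, not that the study's conclusion would be overturned.

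**What to change.** In Protocol 5.2 and SAP 2.2.4:
- Separate withdrawal of consent from discontinuation decided by the physician or prompted by an event.
- State that only death or the subject's own withdrawal of consent ends the scheduled telephone contacts. Leave the existing rule on missed contacts and loss to follow-up as it is.
- At consent withdrawal, ask whether the subject permits vital-status and medical-record checks at 3 years.
- Reconcile the text with Protocol 11.1.1 on following adverse events to resolution.

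Keep the reasons in SAP Table 4. Deleting them would not prevent such exits and would hide what a reader needs to judge whether censoring is informative.

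The cost is a wording change, an edit to the exit form and a few more telephone calls. SAP version 3.2 is dated June 2020, and Protocol 10 projected the last 3-year follow-up for October 2019, so some contacts may no longer be possible. For subjects already exited, record and vital-status checks where consent allows, with exit reasons reported, would recover part of the benefit.

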**Figure 1: Study Flowchart**

## 6 Criteria of Eligibility

### 6.1 Inclusion Criteria

Prior to enrollment in this study, candidates must meet **ALL** of the following criteria:

#### 6.1.1 General Inclusion Criteria

1. Subject is  $\geq 18$  years old.
2. Subject is eligible for percutaneous coronary intervention (PCI).
3. Subject is eligible for dual anti-platelet therapy (DAPT) with aspirin plus either clopidogrel, prasugrel or ticagrelor for a minimum of 1 month.
4. Subject understands the nature of the procedure and provides written informed consent prior to the catheterization procedure.
5. Subject is willing to comply with specified follow-up evaluation and can be contacted by telephone.
6. Subject is an acceptable candidate for coronary artery bypass graft (CABG) surgery.
7. Subject has stable angina pectoris (Canadian Cardiovascular Society Classification [CCSC] 1, 2, 3 or 4) or unstable angina pectoris (Braunwald Class 1-3, B-C) or a positive functional ischemia study (e.g., exercise tolerance test [ETT], single-photon emission computerized tomography [SPECT], stress echocardiography or cardiac computerized tomography [CT]).
8. Female subjects of child bearing potential must have a negative pregnancy test within 7 days prior to enrollment in the study.

#### 6.1.2 Angiographic Inclusion Criteria

1. Subject is indicated for elective stenting of a single stenotic lesion in a native coronary artery.
2. Reference vessel  $\geq 2.5$  mm and  $\leq 4.0$  mm in diameter by visual estimate.
3. Target lesion  $\leq 30$  mm in length by visual estimate (the intention should be to cover the whole lesion with 1 stent of adequate length).
4. Target lesion stenosis  $\geq 50\%$  and  $< 100\%$  by visual estimate.

### 6.2 Exclusion Criteria

Candidates must be excluded from this study if **ANY** of the following criteria is met:

#### 6.2.1 General Exclusion Criteria

1. Subject is currently enrolled in another investigational device or drug trial that has not completed the primary endpoint or that clinically interferes with the current study endpoints.
2. Subject was enrolled in another stent trial within 2 years prior to the index procedure.
3. Any planned elective surgery or percutaneous intervention within nine (9) months post- procedure.

4. A previous coronary interventional procedure of any kind within 30 days prior to the procedure.
5. The subject requires staged procedure of either the target vessel or any non-target vessel within 9 months post-procedure.
6. The target lesion requires treatment with a device other than percutaneous transluminal coronary angioplasty (PTCA) prior to stent placement (such as, but not limited to, directional coronary atherectomy, excimer laser, rotational atherectomy, etc.).
7. Previous drug-eluting stent (DES) deployment anywhere in the target vessel.
8. Any previous DES deployment within the past 12 months.
9. Any previous stent placement within 15 mm proximal or distal to the target lesion.
10. Co-morbid condition(s) that could limit the subject's ability to participate in the trial or to comply with follow-up requirements, or impact the scientific integrity of the trial.
11. Concurrent medical condition with a life expectancy of <3 years.
12. Documented left ventricular ejection fraction (LVEF) <25% at the most recent evaluation.
13. Evidence of an acute MI within 72 hours of the intended index procedure.
14. History of cerebrovascular accident or transient ischemic attack within 6 months prior to the index procedure.
15. Leukopenia (leukocytes  $<3.5 \times 10^9/\text{liter}$ ).
16. Neutropenia (absolute neutrophil count  $<1,000/\text{mm}^3$ )  $\leq$  within 7 days prior to enrollment.
17. Thrombocytopenia (platelets  $<1,00,000/\text{mm}^3$ ) (within 7 days prior to enrollment).
18. Active peptic ulcer or active gastrointestinal (GI) bleeding.
19. Subjects who are ineligible for  $\geq 1$  month of DAPT because of bleeding diathesis or any other reason.
20. Known hypersensitivity or contraindication to aspirin, thienopyridine, both heparin and bivalirudin, cobalt, nickel, L-605 cobalt-chromium alloy or sensitivity to contrast media that cannot be adequately pre-medicated.
21. Serum creatinine level  $>2.5 \text{ mg/dL}$  within 7 days prior to the index procedure.
22. Subject was previously enrolled in the PIONIR Study or the NIRTRAKS Post-Market Study.

